We carefully considered the inclusion of transgender youth or YMSM that identify along the transfeminine spectrum but decided against it based upon our extensive clinical and research experience with this population. The underlying mechanisms of risk that lead to the acquisition of HIV are considerably different for transgender youth in comparison to the YMSM age 13-18 that this RFA seeks to target.⁵⁶ As one example, the literature on HIV acquisition and risk among young transgender women suggests that engagement in commercial sexual acts is a leading factor for the acquisition of HIV. In one study, young transgender women ages 16-24 with a history of engagement of commercial sex had a 23% prevalence of HIV versus 6% among those without a history of commercial sex

engagement. This risk factor is far less prevalent among YMSM. More to the point, the construct of commercial sex for transgender youth is complex in that it may affirm a gender identity for youth who often have difficulty identifying sexual or romantic partners as well as providing strong financial incentives (particularly for condomless anal sex) for a population of young people who face extreme degrees of economic marginalization.⁵⁷ Simply stated, YMSM ages 13-18 do not experience the same social forces. As such, we do not believe MyPEEPS Mobile (or any behavioral intervention) can be adequately culturally responsive to the HIV prevention needs of both adolescent YMSM and young transgender women or those who identify along the trans-feminine spectrum.⁵⁸⁻⁶¹

Participant exclusion criteria. Males are ineligible to participate in the trial if: 1) they are HIV positive; 2) investigators determine that participation may be detrimental to the participant or to the study (e.g., severe cognitive deficit); or 3) they participated in the pilot phase of the project.

B. Study Aims

B.1. Specific Aim 1: Using qualitative methodology and usability assessments, update and translate the MyPEEPS intervention into MyPEEPS Mobile for diverse YMSM.

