We will recruit 900 participants. We will no longer be limiting our participants to these study sites and have expanded to include study participants from across the US. Using active and passive recruitment methods, the on-site project coordinator at each site will oversee and participate in recruitment efforts. The study staff hired through this project, on-site coordinator and the peer-to-peer networking efforts at each site will be used to recruit study participants. Each of our sites have previously participated in recruitment efforts for projects similar to the one proposed here and will be able to successfully recruit the study sample for this project. Our study participants will all have face-to-face contact with our study staff as a means to verify participants' identity. In order to accomplish this using an online sample, we will verify participants' identity using video conferencing (i.e. Zoom). Note: As per the RFA, we will ensure that we have an adequate number of participants in each age group (e.g., 13 year olds) to conduct valid sub-group analyses. Based on our power analysis, we will recruit at least 70 participants in each age.

C.3. Procedures for Maximizing Research Integrity.

To Maintain Blind Assessment, we will collect data through electronic surveys on tablet computers. Interviewers will remain in the room to ensure comprehension. Electronic survey completion offers several advantages: (1) It yields more accurate responses than face-to-face interviews about sensitive topics. (2) Participant can complete measures at their own pace. (3) Questions are answered privately increasing anonymity. (4) The interview structure permits skipping follow-up questions when the stem is answered negatively. (5) Computer delivery ensures uniform administration. Procedures for Maximizing Retention. We will use multiple strategies to reduce attrition.^{79,80} At baseline and follow up interviews, we will update contact information and encourage ongoing communication. We will offer multiple reminders via text, email or calls, based on participants' preference. To ensure follow-up assessments can be conducted for those who move, we will provide access to the assessment via link into a secure server, where data is encrypted at entry and no identifiers are collected.

C.4. Description of study population.

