study at selected activities and social events sponsored by our community partners. When making presentations at selected events, the recruiter making the presentation will provide a brief background on the study, and invite all potential participants who are interested to speak to one of the study recruiters. With permission from local high schools, we will conduct community presentations and provide study flyers; thus far, we have letters from Broome Street Academy and Peer Health Exchange. We will also seek approval to present at LGBT events sponsored by programs such as Planned Parenthood.

Department of Health Clinics, Medical Clinics, and FQHCs: The study sites have strong ties to the public health community and will be able to advertise for the study in various clinics that serve the target population. Specifically, Columbia University and PHS will be able to advertise via flyers for the NYC study site at Columbia University Medical Center, as well as NYC DOHMH STD and HIV clinics (please see Letters of Support), and APICHA which serves racially/ethnically diverse MSM with an emphasis on Asian and Pacific Islanders (See Letter of Support). Chicago is equally well-connected to health clinics and youth resources such as the Peer Health Exchange (e.g. Chicago public schools), the Broadway Youth Center of Howard Brown Health, Illinois Safe Schools Alliance, Illinois Caucus for Adolescent Health, TPAN, BYC, Northwestern on Belmont, U of C Medical, South Side Health Center, and VIDA/SIDA. The Alabama site will recruit from their main CBO in Birmingham, Birmingham AIDS Outreach, through Advocates for Youth Birmingham. Seattle has strong relationships with Harborview public clinic and STI/HIV clinic, and Gay City community LGBTQ center.

Newspaper Advertisements: We will advertise the study through the placement of ads in a variety of free newspapers widely distributed throughout cities across the four study sites.

Craigslist Advertisements: We will post free daily ads on Craigslist

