Participant eligibility will be confirmed in person prior to obtaining informed assent/consent. For participants who are enrolled online, we will also use a form of video conferencing (eg. Zoom, etc) so that participants can show an ID and verify their identity.

C.8.2. Informed assent/consent.

Upon arrival at the enrollment visit we will collect written informed consent (18 year olds) (assent for 13-17 year olds) for enrolling men into the study trial (See Protection of Human Subjects and Inclusion of Children). The informed consent form provides details of the study procedures, risks, benefits, site contact information, and the nature of confidentiality and voluntary participation. The consent process also covers information on the trial and compensation for time. A baseline visit will be conducted involving a behavioral assessment (see questionnaires in Appendix A). The baseline assessment is expected to last approximately 1.5-2 hours and participants will be given \$25 as a token of appreciation for their time. YMSM will then be randomized to the intervention or delayed intervention

arm.

C.8.3. Randomization to intervention and delayed intervention study arms.

Using the randomization approach described below, there will be random or minimally biased assignment of subjects to study arms. We will use block randomization for this study,⁸² stratified by site and each category of study participants with have randomly permuted blocks to reduce opportunities for selection bias we will use a variable permuted randomization block design where the block size itself is randomly selected (i.e., blocks of four to eight). The advantage of the permuted block design is that treatment assignment is predetermined before the trial begins and then assignment remains static throughout the course of the trial.⁸³ Blinding and random assignment will be maintained through continuous supervision by key members of the research team. All staff, and participants will be kept blinded to outcome measurements during data collection.⁸⁴ This technique will maintain complete randomness of the assignment of a subject to a particular group. Participants will be randomized based on the use of computer-generated random numbers at baseline.

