The randomization database will be stored on a password protected computer at Columbia University and will only be accessible to [name] and the project manager at Columbia University to avoid the possibility of the study sites subverting randomization as has been noted in previous studies.⁸⁵ Following completion of the informed consent and baseline assessment, participants will be randomly assigned to one of the two trial arms using sequentially numbered, opaque, sealed envelopes containing the intervention assignment, which the staff member opens at the moment of randomization.⁸³ This will minimize the biased assignment of study subjects which meets the PRS Efficacy Criteria for Best Evidence Risk Reduction Individual Level -Tier 1.⁸⁶ This will ensure against accidental bias and produce comparable groups in all respects except the intervention each group received.⁸⁷ If the study participant is randomized to the intervention arm, they will have access to the MyPEEPS Mobile for the next three months. Participants randomized to the delayed intervention arm will not have access to MyPEEPS Mobile and will be asked to complete their surveys every 3 months and will be provided access to the app at 9 months.

Participants in both groups will complete a baseline assessment (Appendix B) at time 0. Through our system, we will be able to monitor when participants login to MyPEEPS Mobile, time spent on each module and whether they are actively using the intervention or just logged in.

For participants enrolled online, once they are consented, we will then email them the baseline survey through Qualtrics and send them a login in to the app if they are in the intervention group. If they have not logged into the app within 24 hours after enrollment, we will call them to follow up.

C.9. Overview of data collection time points.

We will conduct simultaneous assessments for both intervention arms at three-month intervals starting with a common baseline through six-month postintervention follow-up (Figure 5). We will also collect an immediate post-intervention assessment for Best Evidence Risk Reduction Individual Level -Tier 1.⁸⁶

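### C.8.3 uses a recognised concealment method, but it does not separate the Columbia list holders from New York enrolment, and online the arm can be known before baseline is complete

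*Combined protocol and SAP*

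**What the plan says.** **Who holds the list.** Under C.8.3, "The randomization database will be stored on a password protected computer at Columbia University". Only one person (name removed from the public text) and "the project manager at Columbia University to avoid the possibility of the study sites subverting randomization" can open it.

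**How the arm is released.** C.8.3 uses permuted blocks stratified by site and participant category, "where the block size itself is randomly selected (i.e., blocks of four to eight"). After consent and the baseline assessment, the arm is released from "sequentially numbered, opaque, sealed envelopes containing the intervention assignment, which the staff member opens at the moment of randomization". C.8.2 gives the same order for the enrolment visit: consent, baseline, then randomisation.

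**Who recruits.** C.2 says that "the on-site project coordinator at each site will oversee and participate in recruitment efforts". For New York, C.7.a adds that "Columbia University and PHS will be able to advertise via flyers for the NYC study site at Columbia University Medical Center".

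**The online route.** The last paragraph of C.8.3 says that, once online participants have consented, staff email the baseline survey and send an app login to those in the intervention group. The end of C.1 says that, after identity is verified by video, staff send links to the consent form and baseline survey together with the app login. Neither place mentions an envelope, or a check that the survey is complete before the arm is known.

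**The concern.** The plan sets its own standard: the sites must not be able to see the list. Giving the list to Columbia meets that standard for Birmingham, Chicago and Seattle. New York is different because Columbia takes part in recruiting there, and the plan does not say that the two holders stay out of screening, consent and enrolment at that site. It also does not say who fills, stores, logs or audits the envelopes.

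The online route is the second gap, and it matters more now that C.2 and C.8 open recruitment to the whole country. If an app login goes out with or before the baseline survey, two things can happen. Whether a youth completes baseline can depend on the arm, and the baseline answers can be given by someone who knows the arm or has already used the app.

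At stake are comparability at entry and the validity of wave 0, on which the analysis model relies. The arm is visible after assignment, because delayed participants have no app until 9 months, so staff can build up a history from which to guess. There is some discretion at entry: exclusion 2 in A.3 applies when "investigators determine that participation may be detrimental to the participant or to the study".

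**Working it through.** The plan gives no figure on this point to reproduce. The check sets the passages side by side and then asks how predictable the sequence is and what steering could do.

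**1. Order of events by route**

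| Step | C.8.2 and main text of C.8.3 | Online paragraph of C.8.3 | End of C.1 |
|---|---|---|---|
| Consent | first | first | link sent after identity check |
| Baseline survey | completed second | emailed after consent | link sent with consent form |
| Arm released | third, by envelope | login sent to intervention arm, same sentence as survey; no envelope | login sent with the other links; no envelope |

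Read literally, the online paragraph lets the arm be known before baseline is complete, and C.1 lets it be known before consent. Both conflict with the main rule of C.8.3.

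**2. Predictability.** Assumptions: 1:1 allocation; block sizes 4, 6 and 8 equally likely (the text gives only a range of four to eight); every past arm in the stratum known. The guesser always names the arm that is behind and tosses a coin when the arms are level. In a block of size 2m the expected number of correct guesses is m + (4^m / C(2m,m) − 1)/2.

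- Size 4: 2 + (16/6 − 1)/2 = 2.833, or 70.8%.
- Size 6: 3 + (64/20 − 1)/2 = 4.100, or 68.3%.
- Size 8: 4 + (256/70 − 1)/2 = 5.329, or 66.6%.
- Mixture: (2.833 + 4.100 + 5.329)/(4 + 6 + 8) = 12.262/18 = 68.1%.

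Simulation agrees: 67% in a stratum of 20 and 68% in a stratum of 225 (900/4). Pure chance is 50%.

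**3. Certain assignments.** I tracked the block positions compatible with the observed history while the block size stays unknown. The share of assignments that could be known with certainty was 2.3% to 2.4% for sizes 4, 6 and 8. If only sizes 4 and 8 were in use it would be 6% to 8%.

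**4. Illustration of steering.** Assume half the sample has a mean of 1.8 acts and half 0.6, which averages to the baseline mean of 1.2 in C.5. If a share s of entries is steered with accuracy a, the high-risk share in one arm is 0.5 + s(a − 0.5).

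- s = 0.10 by guessing, a = 0.68: share 0.518; arm means 1.222 and 1.178; ratio 1.037.
- s = 0.10 with the list, a = 1: share 0.55; arm means 1.26 and 1.14; ratio 1.105.

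**5. What the planned analysis does with that shift.** Take the larger case with the planned ratio of 0.73 (C.5). If high-risk youths are steered into the intervention arm, the raw follow-up ratio is 0.73 × 1.105 = 0.81. Dividing by the baseline ratio returns 0.81/1.105 = 0.73. The C.14 model includes the baseline wave and a separate Arm term, so a difference that is constant over time goes largely there and not into the intervention coefficient. This protection needs the difference to be stable and the baseline to be unaffected by knowledge of the arm. The online route puts the second condition in doubt.

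**The case against.** The strongest reply is that the design is already sound. Computer-generated allocation in randomly sized blocks, released from numbered sealed envelopes after consent and baseline, is an accepted method. Opening an envelope reveals that participant's arm and not the next one. An open trial concerns blinding after assignment, not concealment before it. This stands, and a reader who infers that allocation is not concealed goes further than the documents allow.

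The reply continues that no passage gives the project manager an enrolment task, that site recruitment belongs to on-site coordinators, and that the other holder's role cannot be read because the name was removed. This also stands: it is only an inference that a list holder enrols New York youths. The point is limited to the absence of any stated separation at a site that Columbia helps to recruit for.

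Three other tempting readings fail:

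- A figure of about 25% certain assignments holds only if the block size is known. The expected forced assignments are then (1.333 + 1.5 + 1.6)/18 = 24.6%, but the plan randomises the size.
- It is not true that nothing later would reveal steering. The behavioural outcomes are measured at baseline (Table 3), so steering on them would show as imbalance. C.8.1 keeps a count of eligible youths and declines. C.9 adds a medical-record review where records are available.
- The shift of about 10% in raw arm means is not the bias in the planned estimate, for the reason in step 5 of the working.

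The 68% also needs complete tracking of each stratum, which the plan does not say staff would have. Exclusion 2 is an investigator decision, and eligibility is confirmed before consent (C.8.1.a).

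None of this answers the conflict over the order of events online.

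**Conclusion.** The concern holds in a limited form. Concealment is sound in method, but it is not documented as independent of enrolment at New York. For online enrolees the text contradicts the plan's own rule that assignment follows consent and a completed baseline.

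Predictability is modest: about 68% correct guesses against 50%, with about 2% of assignments certain. This rests on full knowledge of past arms and on blocks of 4, 6 or 8 being equally likely. Steering 10% of entries would move the ratio of raw arm means by about 4% by guessing and about 10% with the list, under the assumed 1.8/0.6 split. The bias in the planned estimate would be smaller if the shift is stable and baseline is clean. The documents do not say how many participants enrol online, so the reach of the second weakness cannot be sized.

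This is a worthwhile and inexpensive improvement. It is not evidence that allocation was or will be subverted.

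**What to change.** In C.8.3, for all participants:

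- Replace the envelopes with central allocation in REDCap, which the trial already uses for screening and online consent. The table is loaded and held by a statistician with no role in recruitment or its supervision.
- Release each arm only after eligibility, consent and a completed baseline survey are logged with a time stamp. The baseline survey runs in Qualtrics, so its completion must be passed to or entered in REDCap.
- Rewrite the online paragraph of C.8.3 and the end of C.1 to follow that order, so that the app login is sent only after release.
- Keep block sizes out of site-facing documents.

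For anyone already enrolled online, compare the time of baseline completion with the first app login, which the system records, and report how many logins came first.

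The cost is a short amendment and a one-off set-up in existing software, with no extra participants or visits.

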the intervention, since we have additional data points we have additional power to detect significant differences between both the intervention and delayed intervention group as well as a pre-posttest difference within groups. The multiple data points that we will collect from our delayed intervention group before exposure to the intervention will allow us to control for selection-history. This is particularly relevant for in the case of a mobile intervention since the mobile app marketplace is rapidly evolving and changing and so a new HIV prevention app may enter and/or leave the marketplace during our study. We will be able to control for this historical bias with our study design. While we have systems in place during our randomization to control for assignment bias, this threat to validity can still exist. Since both groups will receive the intervention, there is a mitigated risk for assignment bias.⁹⁰ Finally, we will be able to assess the 3 and 6 month effect of the intervention. The intervention outcomes are based on the content of the MyPEEPS Mobile intervention and match those from the MyPEEPS pilot. The study design, assessments, and intervention delivery time points are delineated

in Figure 5. The trial includes screening, baseline assessment, a 3 month MyPEEPS Mobile intervention and 3 and 6-month follow-up assessments. Recruitment for the study trial will last approximately 2.5 years. Participants will be able to attend the baseline visit in person or can set up a video chat (eg. skype, zoom, facetime call) through which we will verify participants identity and then we will send them a link to the e-consent form, baseline survey and login for the app.

C.2. Sampling approach to successfully enroll YMSM participants in this national project.

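### For remote enrolment, C.1 and C.8.3 contain no step that holds allocation or the app login until the baseline survey has been submitted

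*Combined protocol and SAP*

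**What the plan says.** The general order is clear and is given twice. After describing consent and the baseline assessment, C.8.2 says "YMSM will then be randomized to the intervention or delayed intervention" arm. C.8.3 repeats it: "Following completion of the informed consent and baseline assessment, participants will be randomly assigned to one of the two trial arms", using sealed envelopes that a staff member opens at that moment.

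The remote route is described in two places.

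- C.8.3, on the online route: "once they are consented, we will then email them the baseline survey through Qualtrics and send them a login in to the app". The sentence goes on to limit the login to one arm: staff "send them a login in to the app if they are in the intervention group". It is followed by "If they have not logged into the app within 24 hours after enrollment, we will call them to follow up".
- C.1, for a baseline visit held by video chat: identity is verified, and "then we will send them a link to the e-consent form, baseline survey and login for the app".

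On timing, C.8.3 adds only that "Participants in both groups will complete a baseline assessment (Appendix B) at time 0". It gives no deadline for the emailed survey and no check that it has been submitted.

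In the analysis (C.14, Table 4), the intervention indicator I is 0 before and 1 after the intervention, and its coefficient is named as the main outcome measurement.

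**The concern.** A baseline measures the pre-intervention state only if it is answered before the participant knows the allocation and before any exposure. The general rule secures this. The remote text does not restate the rule, and the trigger it gives is consent, not a submitted survey.

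The outcomes are self-reported. Someone who has just been given the app, or who has already worked through some of it, may report recent behaviour differently. The primary counts use a 3-month recall (C.11.a), so brief exposure could move them mainly through reporting. Intentions, self-efficacy and the time-varying knowledge covariate in C.14 are more open to change. Exposure before baseline can occur only in the intervention arm, so any resulting error would differ by arm.

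Online enrolment is not a side route: C.2, C.7.a and C.8 extend recruitment to the whole United States.

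**Working it through.** No stated figure depends on this point, so the check is a comparison of the text.

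1. **Order under the general rule (C.8.2, C.8.3).** Consent, then completed baseline, then randomisation, then app access for the intervention arm. No online exception is stated.

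2. **Order under the online sentence (C.8.3).** Consent, then survey emailed and login sent to the intervention arm. A login limited to one arm requires the allocation to be known when the login is sent. The sentence does not say whether the survey has been returned by then. Two sequences therefore fit it:
   - (a) consent, survey sent, survey submitted, randomisation, login;
   - (b) consent, randomisation, survey and login both sent, the participant opening either one first.

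   Sequence (a) satisfies the general rule and (b) does not. Nothing in the online sentence itself excludes (b).

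3. **Order under C.1.** E-consent, survey and login appear as one step, with no condition on arm or on a completed baseline. This is closer to (b), although the list cannot be taken literally, as discussed under the objection.

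4. **The reminder call (C.8.3).** It is timed from enrolment, not from baseline submission or login release. Enrolment is not defined relative to baseline. If it means consent, staff may prompt a participant to open the app while a survey of 1.5 to 2 hours (C.8.2) is still unfinished.

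5. **Comparison with the pilot (B.2.5).** There the app is installed on the phone only after consent and after the baseline surveys are done. The plan thus states such a condition elsewhere, and the remote RCT text lacks it. The envelope procedure is also described only with a staff member opening it, and no remote counterpart is given.

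6. **Weight of baseline in the model (Table 4).** Counting rows by the indicator I:
   - intervention arm: I = 0 at baseline only, and I = 1 at 3, 6 and 9 months, so 1 of 4 rows is pre-intervention;
   - delayed arm: I = 0 at baseline, 3, 6 and 9 months, and I = 1 at 12 months, so 4 of 5 rows are pre-intervention.

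   A baseline answered after app use in the intervention arm would be coded as pre-intervention, and that participant would have no other pre-intervention observation.

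7. **Size.** An estimate would need the proportion enrolled online, the proportion of those whose baseline followed allocation or first login, and the resulting shift in reporting. The documents give none of these.

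**The case against.** The strongest reply is that the online sentence names the survey first and the login second, and that it sits in a section whose general rule already puts randomisation after baseline. Read together, the arm condition on the login simply presupposes that rule. C.1 is weak evidence of order: taken literally it would send a login to every remote participant, which C.8.3 rules out for the delayed arm, and it would send the survey together with the consent link, whereas C.8.3 sends it after consent. C.1 may be only a list of materials, and it concerns a baseline visit with staff contact by video. The reminder call concerns people who hold a login, so it presupposes randomisation, and a survey of 1.5 to 2 hours fits easily within 24 hours.

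Much of this stands. A reader might infer that the plan orders the login to go out with the survey, or that allocation is necessarily known before baseline is complete. The text establishes neither: allocation must be known when the login is sent, not when the survey is sent. A reader might also infer that delayed-arm participants who learn of the wait will skip baseline. That depends on the disputed order and on behaviour the documents do not describe. C.14 plans multiple imputation for missing or partial baseline data.

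The reply does not supply the missing step. The sequential order has to be assumed from the general rule, and site staff who follow the remote text as written could release the login first without departing from it.

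**Conclusion.** The point holds as a gap in procedure that should be closed. The general rule and the two remote descriptions need to be reconciled, because the remote text permits allocation and app exposure before the only pre-intervention observation in the intervention arm. That the gap exists is plain from the text. Whether any site works in the wrong order, and how often, is unknown.

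No numerical bias should be attached to it. A reader might assume a share of late baselines and a reporting shift, and then rescale the intervention arm's own pre/post ratio. Those inputs would be invented, and that ratio is not the model's main parameter: C.14 fits both arms together with terms for arm and wave, and the delayed arm contributes four pre-intervention waves and one post-intervention wave. The conclusion rests only on the wording of C.1, C.8.2 and C.8.3 and on the coding in Table 4.

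**What to change.** In C.1 and C.8.3, state that for remote participants the allocation is revealed, and the login issued to those in the intervention arm, only after the Qualtrics baseline has been submitted. Start the 24-hour call clock at login release.

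Record time stamps for baseline submission, randomisation and first login in both arms, and report by arm how many baselines were submitted after randomisation. Much of this should already be available: C.8.3 says the system monitors logins, and B.2.4 describes audit trails in Qualtrics.

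Do not add an analysis that discards baselines submitted after login. Only the intervention arm has logins at that stage, so this would remove baseline data from one arm on a post-randomisation criterion.

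The cost is a few sentences of protocol text, one hold in the existing workflow, and a short delay before some participants receive the login. The randomisation list and the model are unchanged.
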